#### **Study groups:**

We will enroll n=50 patients with hypoxia (O2 saturation 90% or less on RA) and use clinical data including:

- Room air oxygen saturation
- PaO2/FiO2 ratio 1 hour prior to and then 1, 2, 4, 8, 12 and every 24hours after using AirFIO2.
  - If arterial blood gas result is not available for any time point then the P:F ratio will be imputed using the SpO2.
  - If the patient is on nasal cannula, the estimated FiO2 delivery will be calculated based on the oxygen flow rate in liters per minute (LPM).
- Transition to HFNC or NIV
- ICU transfer
- Ventilator free days
- Survival to discharge
- Cardiovascular (CV) Questionnaire, Cough questionnaire, and Roth score will be completed at baseline, and before discharge by all consented participants and the two questionnaires repeated 1-6 hours after using the device for subjects randomized to receive the AirFIO2.

Additional clinical data pertaining to overall disease severity as measured by the Sequential Organ Function Assessment (SOFA) score and inflammatory markers related to COVID-19 infection will be collected:

- SOFA score
  - Platelet count

- Creatinine
- Mean arterial pressure
- Vasopressor treatment and dose
- Bilirubin
- Glasgow Coma Score (extracted from clinical documentation)
- COVID-19 inflammatory markers
  - D-dimer
  - Ferritin
  - C reactive protein (CRP)
  - Creatine kinase
  - Lymphocyte percentage

These clinical data will be obtained via chart review. For each lab value, the collection time point nearest to study enrollment will be recorded.

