### **Data Analysis & Statistical Considerations**

Sample size calculation was performed, assuming a hypothesized increase in P:F ratio of +25 in the intervention group, no change in P:F ratio in the control group, and standard deviation of 30 in both groups. With these assumptions, for statistical power of 80%, a sample size of 46 subjects will be required. With an expected dropout rate of 10%, a sample size of 50 subjects will be necessary to complete the study.

Groups will be analyzed by intention to treat. Per-protocol analyses will also be performed.

Descriptive statistics will be reported for the overall subject population, and for the two groups.

The primary outcome of intra-subject change in P:F ratio before and after using the device will be analyzed with a paired student's t-test. The absolute change and percent change in P:F ratio will be compared between the control and intervention groups with student's t-tests. A multivariate analysis will be performed comparing the change in P:F ratio using linear regression, controlling for baseline P:F ratio, baseline overall disease severity (SOFA), and baseline COVID-19 related disease activity markers.

Secondary outcomes of risk for high flow nasal cannula, noninvasive ventilation, invasive ventilation will be compared between the intervention and control groups with the  $\chi^2$ -squared test. Survival to discharge will be compared with the  $\chi^2$ -squared test. Logistic regression analysis will be performed for each of these outcomes, controlling for baseline P:F ratio, baseline overall disease severity (SOFA), and baseline COVID-19 related disease activity markers.

Ventilator-free days will be compared using the student's t-test for bivariate analysis, and linear regression for multivariate analysis, controlling for baseline P:F ratio, baseline overall disease severity (SOFA), and baseline COVID-19 related disease activity markers.

Secondary outcomes of questionnaires related to subject symptoms before and after using the device will be analyzed for intra-subject change in questionnaire scores using paired student's t-tests. A multivariate analysis will be performed comparing the change in questionnaire scores using linear regression, controlling for baseline questionnaire score, baseline P:F ratio, baseline overall disease severity (SOFA), and baseline COVID-19 related disease activity markers.

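### As the Study groups section is written, the CV and cough questionnaires are repeated at 1–6 hours only in the device arm, so the 1–6 hour symptom change has no concurrent control

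*Combined protocol and SAP*

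**What the plan says.** **Collection.** Under Study groups, the CV questionnaire, the cough questionnaire and the Roth score "will be completed at baseline, and before discharge by all consented participants". The same sentence then has "the two questionnaires repeated 1-6 hours after using the device for subjects randomized to receive the" device. The Control section gives that arm usual care and mentions no questionnaire at 1–6 hours.

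The Study Schedule table in the Study Summary marks the CV and LCQ rows (LCQ is taken here to be the cough questionnaire) at baseline, between 1 and 6 hours, and at discharge. It has no arm column for any row.

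**Analysis.** Data Analysis & Statistical Considerations covers "Secondary outcomes of questionnaires related to subject symptoms before and after using the device". These "will be analyzed for intra-subject change in questionnaire scores using paired student's t-tests". It adds a multivariate analysis "comparing the change in questionnaire scores using linear regression, controlling for baseline questionnaire score" and further baseline variables. No time point and no arm term are named. For the P:F ratio the same section also specifies a between-group t-test on change; for the questionnaires it does not.

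**The concern.** The first secondary objective asks whether the device improves dyspnea-related symptoms and comfort. That is a causal question, and the trial is randomised so that such questions can be answered against a control.

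If only device patients are asked again at 1–6 hours, the change in their scores combines the device effect, the natural course over those hours, whatever other care the treating physicians give, and the effect of being asked again. A paired test measures that total. The documents do not show which way symptoms move over 1–6 hours. If they improve anyway, the paired test can show a benefit that the device did not cause. If they worsen, it can hide a real benefit or suggest harm. Control scores that were never collected cannot be recovered by modelling.

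**Working it through.** **1. Which comparisons the text allows.**

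| Change in score | Device arm | Control arm under Study groups | Control arm if the schedule applies to both arms |
|---|---|---|---|
| Baseline to 1–6 h | yes | no | yes |
| Baseline to discharge | yes | yes | yes |

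Under Study groups, only the first row lacks a control. In that row the regression could contain device patients only, so it could not estimate an arm difference however it is specified.

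**2. Is the missing arm term peculiar to the questionnaires?** No. The other models are described in the same way: "comparing the change in P:F ratio using linear regression, controlling for baseline P:F ratio"; "Logistic regression analysis will be performed for each of these outcomes, controlling for baseline P:F ratio"; and, for ventilator-free days, "linear regression for multivariate analysis, controlling for baseline P:F ratio". None names an arm term. A between-arm model may therefore be intended throughout.

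**3. The plan's own figure.** The sample size is built on P:F change: difference 25, SD 30, power 80%. Assuming two-sided 0.05 and 1:1 allocation (neither is stated), n per arm = 2 × (1.960 + 0.842)² × (30/25)² = 22.6, rounded up to 23, so 46 in total. This matches the plan. There is no corresponding figure for the questionnaires. With 50 enrolled and 1:1 allocation, each arm has 25.

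**4. Paired test with no device effect.** Assumed, not in the documents: normal change scores, two-sided 0.05, and a drift of d SDs of the change score. The test statistic is noncentral t with n − 1 degrees of freedom and noncentrality d√n. For n = 25 the noncentrality is 0.833, 1.667 or 2.500 for d = 1/6, 1/3 or 1/2, and the critical value is 2.064. Probability of a significant result:

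| n in device arm | d = 1/6 | d = 1/3 | d = 1/2 |
|---|---|---|---|
| 20 | 0.109 | 0.294 | 0.565 (0.5645, so 56%) |
| 23 | 0.119 | 0.334 | 0.630 |
| 25 | 0.126 | 0.360 | 0.670 |
| 30 | 0.143 | 0.423 | 0.754 |

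Nearly all of this lies in the direction of the drift. At n = 25 the opposite tail is 0.0029, 0.0002 and below 0.0001.

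**5. Paired test with a true benefit of 0.5 SD and opposing drift, n = 25.** The net shift is 0.5 − d. The probability of a significant benefit is 0.670 without drift, then 0.360, 0.123 and 0.025 for d = 1/6, 1/3 and 1/2. In the last case the net shift is zero, so 0.025 is simply the one-sided error rate.

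**6. Unadjusted between-arm t-test on change, 25 per arm.** Shared drift cancels: (effect + d) − d = effect. In 100,000 simulations with shared drift from −1/2 to +1/2 SD, total false positives were 0.049–0.051. For a true 0.5 SD the noncentrality is 0.5 × √(25/2) = 1.768 on 48 degrees of freedom, with critical value 2.011 and power 0.410. At 80% power the detectable difference is 0.809 SD with 25 per arm and 0.845 SD with 23 per arm.

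**7. What a control does not remove.** If the shift occurs only in the device arm, as device-specific expectation would, the between-arm test with 25 per arm is significant in 0.089, 0.211 or 0.410 of trials for 1/6, 1/3 or 1/2 SD.

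**The case against.** **The schedule may already provide the control scores.** If the Study Schedule table governs, controls are asked at 1–6 hours and only wording needs repair. This stands as a possibility. But the table has no arm column for anything, so it does not clearly override a sentence that separates all participants from those randomised to the device.

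**A randomised symptom comparison survives.** Both arms complete the questionnaires at baseline and before discharge. This stands, and it limits the point. That comparison covers only patients discharged alive, at patient-specific times, while survival and length of stay are themselves secondary outcomes. It does not answer the 1–6 hour question.

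**The before-and-after wording is the plan's usual style.** The primary P:F outcome is described in the same way, with a paired t-test. This stands as far as it goes, but P:F also gets an explicit between-group test.

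**The percentages are generic.** They would hold for any paired test of that size, and the drift sizes are chosen. Agreed: they show how the test behaves, not what will happen in this trial.

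**The controlled comparison has modest power.** Also true: about 41% for 0.5 SD without adjustment. The paired test's apparent advantage is power for total change, not for the device effect.

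A reader might infer three stronger things. One is that the symptom objective has no randomised comparison at all; the discharge scores contradict this. Another is that the questionnaire regression leaves out arm by design; no regression in the plan names arm, so that cannot be concluded. The third is that the paired test will favour the device; the documents give no direction of drift.

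**Conclusion.** The point holds for the Study groups section as written and for the 1–6 hour change only. There, the paired t-test cannot isolate a device effect and the regression cannot be between-arm. Whether the trial will actually lack control scores depends on how the conflict with the schedule is settled, so it should not be asserted that none will be collected.

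The size is conditional on assumed drift, normal change scores, two-sided 0.05 and about 25 patients per arm. Under those assumptions, a moderate drift takes the paired test far from its nominal 5%, or removes most of its chance of showing a real benefit. The between-arm power figures belong to an unadjusted t-test; the recommended adjusted model may do better or worse.

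The primary outcome and the sample size are unaffected. The change should be made, because it is cheap and the missing data cannot be recovered later. Even after it, expectation specific to the device remains possible in an unblinded trial.

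**What to change.** 1. **Reconcile Study groups with the Study Schedule table** by collecting the CV and cough questionnaires in controls as well, at a time matched to the device arm.
2. **State a time origin that is defined in both arms** and keeps device-arm scores 1–6 hours after first device use. One option is first device use in the device arm and, in controls, a pre-specified equivalent clock time after randomisation. Counting from randomisation alone in both arms is not safe: training and handover follow randomisation with no stated interval, so some device-arm scores could precede device use or come too soon after it.
3. **In Data Analysis & Statistical Considerations**, add an explicit arm term to the questionnaire regression, which is already adjusted for baseline score. Make that between-arm estimate the inferential symptom analysis at 1–6 hours, and keep the paired t-tests as descriptive within-arm results.
4. **Name the arm term for baseline-to-discharge change too**, as a supportive analysis with the limits given above.
5. **State that device-specific expectation cannot be excluded** because the trial is unblinded.

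**Cost.** Two questionnaires once more in about 25 controls if allocation is 1:1 (the Randomization section gives no ratio), plus wording; no added patients. The documents give neither the length of the questionnaires nor who administers them, so the workload needs confirming. If collection in both arms was already intended, only the Study groups sentence and the analysis text change.

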Study Schedule		
Following prescreening for eligibility, participants will provide consent. It is expected the primary consent will be performed at the in-patient bedside with a study coordinator to facilitate and answer questions.
 
After consent, baseline clinical data will be recorded and study related parameters post consent will be collected
											

Parameter	1 hr pre	baseline	1 hr	2 hr	4 hr	6 hr	8 hr	12 hr	Every 24 hr	discharge	withdraw	death
Sp02	X	X	X	X	X		X	X	X	X		X
ABG	X	X	X	X	X		X	X	X	X		X
P/F	X	X	X	X	X		X	X	X	X		X
NC L/m	X	X	X	X	X		X	X	X	X	X	X
HFNC			Yes /No	Yes /No	Yes /No		Yes /No	Yes /No	Yes /No	Yes /No	Yes /No	Yes /No
NIV			Yes /No	Yes /No	Yes /No		Yes /No	Yes /No	Yes /No	Yes /No	Yes /No	Yes /No
Ventilator free			Yes /No	Yes /No	Yes /No		Yes /No	Yes /No	Yes /No	Yes /No	Yes /No	Yes /No
Roth scale		X								X		
CV		X	(betw een	1 & 6hrs)						X		
LCQ		X	(betw een	1 & 6hrs)						X		
SOFA score		X										
Platelet		X										
Creatinine		X										
MAP		X										
Vasopressor tx		X										
Vasopressor dose		X										
Bilirubin		X										
Glasgow coma scale		X										
COVID-19 inflamm		X										

atory markers											
D-Dimer		X									
Ferritin		X									
CRP		X									
Creatine kinase		X									

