### **Primary objective:**

Determine if use of the AirFLO2 device will reduce hypoxia in patients admitted to the hospital with COVID-19 infection. The aim of our study is to determine whether the use of the AirFLO2 device can improve hypoxia as measured by change between baseline PaO2:FiO2 ratio and repeat PaO2:FiO2 ratio between 1 to 6 hours after using the device.

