### **Randomization**

After consent, subjects will be randomized to the intervention or the control group via randomization software.

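### The rule for dating baseline labs allows draws after randomisation or device use, which exposes the covariate-adjusted regressions but no other analysis

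*Combined protocol and SAP*

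**What the plan says.** The combined protocol and SAP fixes the timing of these covariates in one place. Study groups lists the SOFA components and the COVID-19 inflammatory markers and adds: "These clinical data will be obtained via chart review". The next sentence is the timing rule: "For each lab value, the collection time point nearest to study enrollment will be recorded".

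Three other places bear on it:

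- The schedule in the Study Summary puts SOFA, its components and the markers it lists in the baseline column only. Its introduction reads: "After consent, baseline clinical data will be recorded and study related parameters post consent will be collected".
- Randomization says: "After consent, subjects will be randomized to the intervention or the control group via randomization software". Neither enrolment nor baseline is defined anywhere relative to randomisation or first use of the device.
- Data Analysis & Statistical Considerations specifies regressions "controlling for baseline P:F ratio, baseline overall disease severity (SOFA), and baseline COVID-19 related disease activity markers". This set of covariates appears in the linear model for P:F change, the logistic models for escalation of respiratory support and for survival, the linear model for ventilator-free days, and the linear model for questionnaire scores.

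**The concern.** A covariate in a randomised comparison should be fixed before allocation. A value measured afterwards may already carry part of the device effect, and adjusting for it then removes that part from the estimate. It may also carry differences in later care. That route is open here because the trial is unblinded and other care is left to the treating physicians in both arms.

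The primary endpoint is the repeat "ratio between 1 to 6 hours after using the device", so a lab drawn a few hours after enrolment can fall inside the outcome window. Because no window is set, a marker that is seldom ordered could be taken much later, possibly because the patient had worsened. That matters more for the survival and ventilator-free-day models than for the early P:F endpoint.

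**Working it through.** **1. What the covariates do not touch.** The sample size rests on the section's planning assumption, "assuming a hypothesized increase in P:F ratio of +25 in the intervention group, no change in P:F ratio in the control group", with SD 30 and 80% power. Taking two-sided 5% and 1:1 allocation (neither is stated):

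n per arm = 2 × (1.960 + 0.842)² × 30² / 25² = 2 × 7.85 × 1.44 = 22.6, rounded up to 23, so 46 in total.

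This matches the plan's 46 and uses no covariate. The paired and two-sample t-tests and the chi-squared tests use none either.

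**2. Can a draw after enrolment be the nearest one?** Yes, and how often depends on the timing of draws and consent, which the documents do not give. Two assumed cases:

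- One draw every 24 h, enrolment spread evenly over the day: the later draw is nearer whenever enrolment falls in the second half of the interval, so the share is 12/24 = 50%.
- One draw at 06:00, consent between 09:00 and 17:00: the later draw becomes nearer only after 18:00, so the share is 0%.

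A draw after enrolment is not necessarily after randomisation, and one after randomisation is not necessarily after device use. These shares are therefore upper limits for post-device values.

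**3. Size of the bias in the adjusted P:F model.** Let f be the share of device-arm values drawn after device use, g the shift that the device causes in the covariate (in SD), and b the size of the covariate's slope (P:F units per SD). The adjusted effect moves by about f × g × b. All three inputs are assumed.

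- f = 0 or g = 0: bias 0.
- f = 0.25, g = 0.1, b = 5: 0.25 × 0.1 × 5 = 0.125.
- f = 0.25, g = 0.25, b = 10: 0.625. Simulation with a true effect of 25 gave 24.38.
- f = 0.5, g = 0.3, b = 15: 0.5 × 0.3 × 15 = 2.25.
- Stress case, f = 0.5, g = 0.5, b = 20: 5.0. Simulation gave 20.15.

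The stress case needs a half-SD shift in half of the device-arm values and a slope of 20 against an SD of 30, which is a correlation of 20/30 = 0.67 between the covariate and P:F change. It is shown only to mark the edge.

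**4. Scale.** 2.25 is 2.25/25 = 9% of the hypothesised effect. The standard error of the difference at 23 per arm is 30 × √(2/23) = 8.8, so 2.25 is about a quarter of one standard error.

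No comparable figure can be given for the logistic, ventilator-free-day or questionnaire models, because the documents supply no planning values for them.

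**The case against.** The best defence is that the plan means a true baseline. The schedule shows these items in the baseline column only, apart from the columns for later hours, and the analysis section calls them baseline. The rule permits a later draw but does not require one. If labs are taken early in the morning and a coordinator obtains consent during the working day, the nearest value may always be the earlier one. Many of these labs may also move little within hours.

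Most of this stands as a limit on size. It does not close the gap. A column label shows intent, but the sentence under Study groups is what a chart abstractor will follow, and it directs them to a later value whenever that is closer.

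A reader might go further and infer that the main test of the primary outcome is biased, or that about half of the baseline labs will be post-randomisation. The documents support neither. The t-tests on P:F change do not use these covariates, and the one-half figure is a product of the assumed draw and enrolment pattern.

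A reader might also think the change costs nothing. Under the once-daily pattern with even enrolment, about half of the values would move from a draw 0–12 h after enrolment to one 12–24 h before it. Without a look-back limit a value could be older still, and without a rule for missing values complete-case regression could lose subjects from a trial of 50.

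**Conclusion.** The point holds for the covariate-adjusted linear and logistic regressions only. The timing rule lets a post-randomisation or post-device lab serve as a baseline covariate, and nothing else in the document prevents it.

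The bias cannot be sized from the documents. On moderate assumed inputs it is between 0 and about 2 P:F units. It vanishes if no draws fall after device use, or if the device and later care leave the labs unchanged. Confidence is high that the wording permits the problem and low on how much it would matter. Low severity, cheap to correct.

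The rule speaks of lab values. Mean arterial pressure, vasopressor treatment and Glasgow Coma Score also feed SOFA and have no stated timing rule, so the correction should cover them.

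**What to change.** Replace the timing sentence under Study groups with:

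> For each lab value and SOFA component, the last value collected before randomisation, within a stated look-back window (for example 24–48 h), will be recorded.

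Add to Data Analysis & Statistical Considerations:

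> Subjects without such a value remain in the adjusted regressions, with the missing baseline covariate imputed by a simple method that ignores arm (for example the overall mean, pooled across arms).

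The chart review, visits and sample size are unchanged. The cost is that some covariate values will be older, by up to about a day if labs are drawn once daily, and a few will be imputed. The adjustment will be slightly less precise.

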### **Subject Recruitment and Compensation**

Study participants will be recruited from the COVID-19 positive in-patient population at Duke Hospital.

Subjects will not be compensated for their participation in the trial.

Patients will receive the AirFLO2 which will be collected and destroyed upon discharge from the hospital.

### **Consent Process**

Consent will be obtained by a COVID Core CRC with the participant. No additional consent is required for analysis of clinical data.

### **Randomization**

After consent, subjects will be randomized to the intervention or the control group via randomization software.

### **Intervention**

Intervention subjects will receive the AirFLO2 device and training via video with reinforcement from the coordinator how to use and to self-apply it. Bedside nurses will also be given instructions, access to the study video and verbal training as well, so that they can answer simple questions for the patients.

Initially the CRC will hand device to the patient. Oxygen saturation at baseline will be recorded. The patient will set the PEEP at 5 on the mask, then hold the mask firmly against the face, take a full slow deep breath in, then exhale steadily out until out of breath. Record oxygen saturation. Wait 3-5 minutes then repeat maneuver with PEEP at 10. Record oxygen saturation. Repeat again with PEEP at a setting of 15, then again at 20. The highest O2 saturation achieved with the lowest PEEP is the PEEP setting to use. If oxygen saturation does not change or decreases, leave at PEEP of 5.

All other elements of patient care will be managed by the treating physician(s).

